
 ● Summary measures of the total patient time associated with attendance for the administration of a single dose of ERT (with agalsidase alfa or agalsidase beta) in patients with FD. To include: ● Time spent travelling to and from the hospital or treatment centre ● Time spent collecting ERT from pharmacy (where relevant) ● Time from arrival in hospital/treatment centre to departure ● Time from arrival in hospital/treatment centre to start of ERT infusion ● In addition, if the patient started/delivered their ERT infusion at home following set-up at a primary healthcare centre, the 	
Patient responses to the bespoke study questionnaire:
 
 ● Patient ID ● Date of episode ● Patient employment status (employed full time / employed part time / unemployed / retired / student / home-maker) ● Were they accompanied to the hospital or treatment centre (by a relative or caregiver) or did they attend alone (accompanied / alone) ● Time left home/work to travel to hospital or treatment centre ● Time arrived at hospital or treatment centre ● Time of start of ERT infusion.

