
following will also be included in the total patient time:
 
 Duration of ERT infusion and any home-based post-administration activities. Time spent travelling to and from treatment centre after ERT infusion (only if patient returned to treatment centre after ERT infusion) Time spent at treatment centre after ERT infusion. Summary measures of the total cost to patients (i.e. out-of-pocket expenses) associated with attendance for the administration of a single dose of ERT (to include the costs of travel / parking / subsistence / other costs). Distribution of patient employment status and whether the patient attended the ERT administration visit accompanied by a relative/caregiver or alone. Proportion of patients with work absence due to attendance for this ERT episode and number of paid / unpaid hours absent. 	
 Time left hospital or treatment centre to travel back to home/work. Time arrived back at home/work. 
Whether patient returned to work on the day of the infusion or the following day. If the patient started their ERT infusion at home following set-up at a primary healthcare centre, the following will also be collected:
 
 Start and end time of ERT infusion Start and end time of any post-administration activities. Time left home/work to return to hospital or treatment centre (if relevant) Time arrived back at hospital or treatment centre (if relevant) Time left hospital or treatment centre to travel back to home/work Time arrived back at home/work Did patient take any time off work to attend this ERT episode? If yes, number of paid / unpaid hours absent from work. Number of hours worked during ERT infusion (if relevant). Costs (i.e. out-of-pocket expenses) incurred by the patient that were directly related to this ERT administration episode (to include
--	--

	costs of travel / parking / subsistence / any other costs).
Secondary objective 2: To quantify the total caregiver time costs (i.e. out-of-pocket expenses) and work-related absence associated with accompanying a patient with FD for the administration of a single dose of ERT (with agalsidase alfa or agalsidase beta).	

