
Start and end time of infusion (and pre-medication) preparation activities (note: the following activities [as appropriate] will be included in the total time, but the time for each separate activity will not be recorded]: pre-dispensing prescription review, label generation, collation of items prior to assembly, assembly of item/drug reconstitution, labelling of containers, accuracy check, prescription delivery).
	

ERT Infusion Procedure (and pre-medication) administration:
	
Time patient left – Time patient arrived

	
End time – Start time

Time patient arrived in clinic for ERT administration to begin
 
Time patient left clinic following completion of ERT administration
 
Start and end time of pre-medication administration.
 
Start and end time of ERT infusion.
 
Start and end time of HCP activity for administration of IV agalsidase alfa or agalsidase beta (including administration of pre-medications).
 
Start and end time of HCP activity for patient monitoring during agalsidase alfa or agalsidase beta infusion
 
Post-infusion administration assessment and documentation:
 
Start and end time of HCP activity for post-treatment patient assessment / monitoring.
 
Start and end time of HCP activity for completion of clinical documentation.
 
Other ERT-administration related activities
 
Start and end time of HCP activity for any other ERT administration related activities (specify).
	
End time – Start time
 
End time – Start time
 
End time - start time
 
End time – Start time

--	---

Secondary Objective 1

To quantify the total patient time, costs (i.e. out-of-pocket expenses) and work-related absence associated with attendances for the administration of a single dose of ERT (with agalsidase alfa or agalsidase beta) in patients with FD.

Summary measures of the total patient time associated with
	
--	--

attendance for the administration of a single dose of ERT (with agalsidase alfa or agalsidase beta) in patients with FD.
	
The difference between two time points will be calculated in minutes and will be summarized as per section 2.5 for quantitative variables for the following measures.

Time spent travelling to and from the hospital or treatment centre
	
Time left home – Time arrival at hospital

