
 ○ Time left home/work to travel to hospital or treatment centre ○ Time arrived at hospital or treatment centre 	

Time spent collecting ERT from pharmacy (where relevant)
	

Time from arrival in hospital/treatment centre to departure
	

 ○ Time from arrival in hospital/treatment centre to start of ERT infusion ○ Start and end time of ERT infusion. ○ Time left hospital or treatment centre to travel back to home/work ○ Time arrived back at home/work. 	
Time arrived – Time start of ERT
 
End time – Start time

In addition, if the patient started/delivered their ERT infusion at home following set-up at a primary healthcare centre, the following will also be included in the total patient time
	
Time arrived at home – Time left hospital

Duration of ERT infusion and any home-based post-administration activities.
 
 ○ Start and end time of ERT infusion ○ Start and end time of any post-administration activities. 	
End time – start time
 
End time – start time

Time spent travelling to and from treatment centre after ERT infusion (only if patient returned to treatment centre after ERT infusion)
 
 ○ Time left home/work to return to hospital or treatment centre (if relevant) ○ Time arrived back at hospital or treatment centre (if relevant) 	
Time left – Time arrived

Time spent at treatment centre after ERT infusion.
 
 ○ Time left hospital or treatment centre to travel back to home/work ○ Time arrived back at home/work 	
Time arrived back at hospital – Time left hospital/treatment centre
 
Time left – Time arrived back at home/ work

Summary measures of the total cost to patients (i.e. out-of-pocket expenses) associated with attendance for the administration of a single dose of ERT (to include the costs of travel / parking / subsistence / other costs).
	

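### SAP 2.6 writes five patient-time differences with the sign reversed, and neither document defines total patient time, so adding the listed parts counts the wait twice or omits the post-infusion stay

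*SAP*

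**What the plan says.** SAP 2.6, Secondary Objective 1, starts with a general instruction: "The difference between two time points will be calculated in minutes and will be summarized as per section 2.5 for quantitative variables". It then gives formulas for individual rows.

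- Outbound travel: "Time left home – Time arrival at hospital".
- Arrival to start of infusion: "Time arrived – Time start of ERT".
- Infusion: "End time – Start time".
- Return travel after a clinic visit: "Time arrived at home – Time left hospital". In the extracted table this formula sits beside a neighbouring row, so I match it by its wording.
- Home-infusion branch, second stay at the centre: "Time arrived back at hospital – Time left hospital/treatment centre". The second trip to the centre and the final trip home are also written as departure minus arrival.

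The stay from arrival to departure is a named row in the SAP without a formula, and so is pharmacy collection.

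Protocol 9.6, Table 4, says what total patient time is to include. The list contains travel both ways, pharmacy collection, the interval from arrival to departure and, as a further item, "Time from arrival in hospital/treatment centre to start of ERT infusion". For infusions delivered at home it adds that the "following will also be included in the total patient time". The caregiver list in Table 4 has the same structure. No equation for the total appears in either document. The SAP's only summing instruction belongs to the HCP task times under the primary objective.

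**The concern.** A duration is the later clock time minus the earlier one. The SAP follows that rule for HCP time, for infusion and for clinic-visit return travel. It breaks it for outbound travel, the wait, and the home-infusion second trip, second stay and final return. Those five rows are negative as written.

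The second problem is what makes up the total. The wait lies wholly inside the arrival-to-departure stay, yet Table 4 lists both at the same level. The SAP's formulas leave a different fault: none of them covers infusion end to departure. An analyst has to invent a rule to obtain the length of a visit, and two reasonable analysts could invent different ones.

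Total patient time and total caregiver time are among the main secondary endpoints, and the protocol says the data may be used in HTA submissions. Little downstream would catch an error. SAP 3.2 limits independent review to the primary endpoint, Protocol 9.10 raises no queries on patient- or caregiver-reported data, and the shell tables in the SAP appendix are still to be confirmed.

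**Working it through.** The documents state no figure for total patient time, so there is none to reproduce. The illustrative inputs can be checked against Protocol 9.8.

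**Inputs from Protocol 9.8** (HCP planning ranges, used here only as stand-ins for the patient's wait and post-infusion stay):
- pre-administration 10–30 min, midpoint 20
- post-administration 15–30 min, midpoint 22.5
- infusion 40–60 min (alfa), midpoint 50; 90–180 min (beta), midpoint 135

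Check: 20 + 22.5 + 50 = 92.5 and 20 + 22.5 + 135 = 177.5, which match the overall means in Table 5.

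**Assumed, not in the documents:** travel of 60 min each way, range 15–120.

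**Notation for a clinic visit:** L left home, A arrived, S infusion start, E infusion end, D departed, H back home.

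**Signs as written:**
- outbound L − A: negative
- wait A − S: negative
- infusion E − S: positive
- return H − D: positive
- home-infusion second trip, second stay and final return: all negative

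**Totals at 60 min each way:**

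| Reading | Formula | Alfa (min) | Beta (min) | Error (min) |
|---|---|---|---|---|
| Door to door | H − L | 60 + 20 + 50 + 22.5 + 60 = 212.5 | 60 + 20 + 135 + 22.5 + 60 = 297.5 | – |
| Table 4 list added | (A − L) + (H − D) + (D − A) + (S − A) | 60 + 60 + 92.5 + 20 = 232.5 | 60 + 60 + 177.5 + 20 = 317.5 | +20 |
| SAP formulas as elapsed times, added | (A − L) + (S − A) + (E − S) + (H − D) | 60 + 20 + 50 + 60 = 190 | 60 + 20 + 135 + 60 = 275 | −22.5 |

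Algebraically the second row exceeds H − L by S − A, and the third falls short by D − E. Neither error depends on travel time. On the protocol's ranges they are 10–30 min and 15–30 min. The two readings differ by 20 + 22.5 = 42.5 min at the midpoints (range 25–60). That is 42.5/212.5 = 20% of the alfa visit and 42.5/297.5 = 14% of the beta visit at 60 min each way.

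Over 15–120 min travel each way, the door-to-door total runs from 122.5 to 332.5 min (alfa) and from 207.5 to 417.5 min (beta).

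**Home infusion under a door-to-door definition**, with 60 min per leg and assumed values of 20 min set-up, 22.5 min post-infusion activity and a 15 min second stay:
- first round trip 60 + 20 + 60 = 140
- home interval 50 + 22.5 = 72.5 (alfa) or 135 + 22.5 = 157.5 (beta)
- second round trip 60 + 15 + 60 = 135
- total 347.5 min (alfa) or 432.5 min (beta), with each interval counted once

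**The case against.** A reader might infer that the SAP's total loses all travel time. If the signed formulas are added literally, the result is −60 − 20 + 50 + 60 = 30 min (alfa) or −60 − 20 + 135 + 60 = 115 min (beta). With equal outbound and return legs, that result is the same whatever the travel time. The documents do not support this as the plan. The SAP never tells the analyst to add these rows; it summarises each measure. Its instruction to take the difference between two time points can fairly be read as elapsed time. Negative travel and waiting times would also be obvious in the first table. Nor is return travel always positive: the final return in the home-infusion branch is reversed too.

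A reader might also extend the sign problem to caregivers. The SAP's caregiver section has no signed formulas, so only the Table 4 overlap applies there.

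The better objections concern the components. The SAP does name an arrival-to-departure row, and its label gives both endpoints; used alone, it yields the correct clinic stay. The SAP also sets the wait beneath that row, so the wait may be meant as a sub-interval, and nesting in Table 4 may have been lost in extraction. This is a possible reading, but neither document says that the wait is not to be added.

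The claim that pharmacy time is not collected cannot be settled here. Table 4 shows no such field, but it calls its response categories indicative, leaves the final list to the CRF, and the questionnaires are not in the text reviewed.

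Finally, these endpoints are descriptive, the HCP primary endpoint is unaffected, and the clock times are kept, so mistakes can be corrected at programming. That limits the harm but does not supply the missing definition.

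**Conclusion.** The point stands in this form. Five of the SAP's patient-time differences are reversed and give negative durations as written. Total patient time and total caregiver time have no equation in either document. Adding the Table 4 list counts the pre-infusion wait twice, about 10–30 min too much. Adding only the SAP's patient formulas as elapsed times omits infusion end to departure, about 15–30 min too little.

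The signs, the overlap and the missing formula come directly from the text. The minutes rest on HCP planning ranges standing in for patient waiting and post-infusion stay, and the percentages also rest on an assumed travel time. Cancelled travel is not a consequence of the plan as written.

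**What to change.** 1. Define total patient time and total caregiver time once, in Table 4 and SAP 2.6: clock time back at home or work minus clock time of leaving home or work. For home infusions, add the home infusion and post-administration interval and any second round trip, including the stay at the centre. For caregivers, count these additions only where the caregiver took part, as Table 4 already specifies.
2. Write every difference as later minus earlier.
3. Report travel, wait and clinic stay as descriptive parts, and state that they are not added to the total. Give arrival-to-departure its own formula.
4. For pharmacy collection, either confirm that the questionnaire captures it, adding it only when it is a separate trip, or remove it from the list.
5. For clinic visits, take infusion end from the observer's record, because Table 4's patient questionnaire lists only infusion start. Patients who consent to the questionnaires alone will have no observer record, but the door-to-door total does not need it.

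The cost is a wording change in the SAP and Table 4. The clock times for the total are already in the planned questionnaire dataset. Only pharmacy time might need a new field, and only if it is kept and not already captured.

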9.1.2 Cross sectional evaluation of patient- and caregiver-reported outcome measures

Patients with FD and their caregivers will be asked to complete a series of questionnaires, to include validated measures of HRQoL, wellbeing and work productivity (for patients); and work productivity and the strain of care provision (for caregivers).

Questionnaires were selected based on their ease of use, short time required for completion (in order to minimise the burden on patients), availability in the required languages, and the fact that they have been previously validated in a similar context to our study:

- HRQoL will be assessed using the SF-12 version 2. The SF-12 is a shorter version of the 36 item Short Form Survey (SF-36) that uses 12 questions to measure functional health and wellbeing from the patients' point of view. It is made up of 8 domains: physical functioning, bodily pain, general health, vitality, physical role, role emotional, social functioning and mental health¹⁹. These 8 domains form 2 subscales: physical component summary and mental component summary. The SF-12 was chosen for the present study as it was used in a recent registry of patients with FD²⁰ and is less burdensome for patients to complete than the longer SF-36. It has a short completion time (approximately 5 minutes) and is available in all 4 languages of the study countries.
- Patients' general wellbeing will be assessed using the WHO-5²². It consists of 5 items and the timeframe for responses is based on the previous 2 weeks. The 5 items relate to feeling cheerful, calm, active, rested and being interested in life. The WHO-5 was selected to assess the impact of FD and its treatment on patients' well-being. It is quick and easy to complete (<5 minutes) and score.
- The impact of FD on patients' work lives will be assessed using the WPAI. The WPAI consists of 6 items. The WPAI was chosen for the present study as it is quick to complete (<5 minutes) and is available in all 4 languages of the countries selected in this study.

Caregiver-reported outcomes will be evaluated using the following validated questionnaires addressing work productivity and the strain of care provision:

- The impact of caring for a patient with FD on caregivers' work lives will be assessed using the WPAI specific to caregivers (WPAI:CG)²⁴. The WPAI:CG consists of 6 items and was chosen for the present study as it is quick to complete (<5 minutes) and is available in all 4 languages of the study countries.

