
Summary measures of patients':
 
 • HRQoL (SF-12 scores / responses). • General wellbeing (WHO-5 scores / responses). • Level of fatigue (bespoke Fatigue Likert scale). • Levels of work impairment (WPAI scores / responses). 
Questionnaire scores and/or item responses will be reported using summary statistics, as appropriate to the questionnaire and in accordance with the licensed scoring manual / instructions for use.
	
 • Patient SF-12, WHO-5, Fatigue Likert scale and WPAI responses and dates of completion. For the bespoke Fatigue Likert scale, times (hours and minutes) of completion will also be recorded.

Secondary objective 4: To describe work productivity (measured by the WPAI:CG) and the strain of care provision (measured by the CSI) in caregivers of patients with FD treated with ERT.
	

Summary measures of caregivers':
 
 • Levels of work impairment (WPAI:CG scores / responses). • Levels of strain of providing care for a patient with FD (CSI scores / responses). 	
 • Caregiver WPAI:CG and CSI responses and date of completion.

Questionnaire scores and/or item responses will be reported using summary statistics, as appropriate to the questionnaire and in accordance with the licensed scoring manual / instructions for use.
	

Patients' demographic and clinical characteristics (all patients)
	

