9.9.2 Data analysis

A detailed description of study analysis and reporting will be provided in a separate statistical analysis plan (SAP) to be finalised before data collection is completed. Analyses will be carried out by Open Health using R statistical software, Stata™ (StataCorp LLC) version 14 and Microsoft Excel™. Data will be analysed separately for each participating country and by ERT treatment (agalsidase alfa /agalsidase beta).

The planned statistical analyses are summarised below.

This study is designed to be descriptive in nature; there is no *a priori* hypothesis to be tested and therefore no comparisons between patient subgroups or treatments will be made. Distributions and descriptive statistics of central tendency (medians and arithmetic or geometric means) and dispersion (standard deviation [SD], interquartile range [IQR], range) will be presented for quantitative variables. Categorical variables will be described with frequencies and percentages; where appropriate, distributions, modes, medians, IQR and range will be reported. Where appropriate, 95% confidence intervals (95% CI) will also be presented for means and estimates of proportions. Ordinal variables will be evaluated using either frequencies and percentages or medians and IQR or both depending on the number of possible values for the variable.

Analysis for validated instruments will adhere to the licensed scoring manual. Item and domain scores (if relevant) will be presented.

All percentages will be reported to the nearest whole number; therefore, in reporting study results in tables, figures and associated text, percentages may not add up to 100% due to rounding. For total group/subgroup sizes of less than 10, percentages will not be reported, except under exceptional circumstances. Consideration will be given during data analysis as to whether reporting any of the planned analyses may identify individuals from combinations of variables occurring in very small groups; to preserve participant anonymity such results may be suppressed in the study report and any materials intended for publication.

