2.5 Analysis for descriptive endpoints

This study is designed to be descriptive in nature; there is no *a priori* hypothesis to be tested and therefore no comparisons between patient subgroups or treatments will be made. Distributions and descriptive statistics of central tendency (medians and arithmetic or geometric means) and dispersion (standard deviation [SD], interquartile range [IQR], range) will be presented for quantitative variables. Categorical variables will be described with frequencies and percentages; where appropriate, distributions, modes, medians, IQR and range will be reported. Where appropriate, 95% confidence intervals (95% CI) will also be presented for means and estimates of proportions. Ordinal variables will be evaluated using either frequencies and percentages or medians and IQR or both depending on the number of possible values for the variable.

Analysis for validated instruments will adhere to the licensed scoring manual. Item and domain scores (if relevant) will be presented.

All percentages will be reported to the nearest whole number; therefore, in reporting study results in tables, figures and associated text, percentages may not add up to 100% due to rounding. For total group/subgroup sizes of less than 10, percentages will not be reported, except under exceptional circumstances. Consideration will be given during data analysis as to whether reporting any of the planned analyses may identify individuals from combinations of variables occurring in very small groups; to preserve participant anonymity such results may be suppressed in the study report and any materials intended for publication.

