
Summary measures of patients':
 
 ○ HRQoL (SF-12 scores/ responses) ○ General wellbeing (WHO-5 scores / responses). ○ Level of fatigue (bespoke Fatigue Likert scale). ○ Levels of work impairment (WPAI scores / responses) ○ For the bespoke Fatigue Likert scale, times (hours and minutes) of completion will also be recorded. 	
Questionnaire scores and/or item responses will be reported using summary statistics, as appropriate to the questionnaire and in accordance with the licensed scoring manual / instructions for use.
 
For these scores, the total of all items in each of these will be summarized as per section 2.5 for quantitative variables. The frequency and percentages of responses for individual items will also be given. HRQoL and Who-5 will be given for baseline (the data collected during ERT infusion visit). Fatigue score will be given for baseline and the change scores from baseline to score collected at the same day evening of ERT infusion and 15 days after 1st infusion. WPAI scores will be given one at 1-7 days after infusion and change from this to 15 days after infusion.
 
The summary statistics of completion time in minutes will be calculated as per section 2.5 for quantitative variables.

---	---

Secondary objective 4

To describe work productivity (measured by the WPAI:CG) and the strain of care provision (measured by the CSI) in caregivers of patients with FD treated with ERT.

Summary measures of caregivers':
	
Questionnaire scores and/or item responses will be reported using summary statistics, as appropriate to the questionnaire and in accordance with the licensed scoring manual / instructions for use.

---	---

 ○ Levels of work impairment (WPAI:CG scores / responses). ○ Levels of strain of providing care for a patient with FD (CSI scores / responses). 	
The total scores will be summarized as per section 2.5 for quantitative variables. The individual item responses will be presented using frequency and percentages.
 
WPAI-CG will be summarized at 1-7 days after 1st infusion and change from this to 15 days after infusion.
 
CSI scores collected during ERT infusion will be summarized.

Patients' demographic and clinical characteristics (all patients)	

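### SAP 2.6 asks for an SF-12 item total that neither document defines, and the SAP never names the physical and mental component summaries the protocol describes

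*SAP*

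**What the plan says.** SAP 2.6, under secondary objective 3, lists the SF-12, WHO-5, bespoke fatigue scale and WPAI. It first says that scores and/or item responses will be reported "as appropriate to the questionnaire and in accordance with the licensed scoring manual / instructions for use". The next sentence is specific: "For these scores, the total of all items in each of these will be summarized as per section 2.5 for quantitative variables". Item frequencies and percentages are also planned. For the WPAI the cell adds: "WPAI scores will be given one at 1-7 days after infusion and change from this to 15 days after infusion". The caregiver cell (secondary objective 4) refers to total scores for the WPAI:CG and CSI and plans the same kind of change for the WPAI:CG.

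SAP 2.5 adds a general promise: "Item and domain scores (if relevant) will be presented".

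Protocol 9.1.2 gives the structure of the SF-12 version 2. It has 12 questions in 8 domains, and "These 8 domains form 2 subscales: physical component summary and mental component summary". The protocol endpoint in Table 4 is looser, "HRQoL (SF-12 scores / responses", and is to be reported "in accordance with the licensed scoring manual / instructions for use". Protocol 9.9.2 states: "Analysis for validated instruments will adhere to the licensed scoring manual". The table shells in the SAP appendix are still to be confirmed.

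**The concern.** The item-total sentence is the only explicit derivation rule for an SF-12 score anywhere in the SAP, and it yields a score the protocol does not describe. An analyst who follows it puts one 12-item figure at the head of the HRQoL results. An analyst who follows the manual clause and Protocol 9.1.2 would look to the two component summaries. Both are following the SAP in good faith.

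HRQoL is part of secondary objective 3, and Protocol section 7 says the data may be used in HTA submissions. Without a stated direction, recoding or range, a reader could not interpret a 12-item total. On its own it would not show whether the burden is physical or mental. No planned check would catch this: SAP 3.2 and Protocol 10.1 confine independent review to the primary endpoint and exclude further checks.

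**Working it through.** This is a comparison of texts; no sample-size or precision figure is involved. The table sets what the protocol says about each instrument (9.1.2) beside what SAP 2.6 says to summarise.

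| Instrument | Protocol description | SAP 2.6 instruction | Left open |
|---|---|---|---|
| SF-12 v2 | 12 questions, 8 domains, 2 component summaries | total of items, plus item frequencies | the total is undefined; neither summary is named |
| WHO-5 | 5 items | same | nothing claimed here |
| Fatigue scale | a single item, completed three times | same, plus change scores | there is nothing to total; the time points differ from the protocol |
| WPAI | 6 items, completed twice | same, plus one change | whether the manual defines a total; which score the change uses |
| WPAI:CG | 6 items, completed twice | total scores, plus one change | same as the WPAI |
| CSI | 13 items, five domains | total scores | nothing claimed here |

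1. **Scores the protocol describes for the SF-12:** 8 domains + 2 component summaries = 10.
2. **Scores the SAP covers:** SAP 2.5 reaches the 8 domain scores, generically and only where relevant. The component summaries are named 0 times in the SAP. SAP 2.6 adds 1 total that is not among the 10.
3. **Is that total defined anywhere?** No. Neither document gives item recoding, direction, weights or a range for it.
4. **Does another clause settle the matter?** The manual rule stands in four places that cover the patient instruments: Protocol Table 4, Protocol 9.9.2, SAP 2.5 and the sentence just before the item-total sentence in SAP 2.6. It points to the manual in general terms. The sentence after it gives a particular score without saying that the manual defines it.
5. **Was the sentence written instrument by instrument?** Evidently not, since it also covers a scale with one item.
6. **How many patients:** 4 countries × about 30 = about 120 questionnaire sets. For the WPAI:CG, 4 × about 5 = about 20 caregivers.

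A related point arises in the same cell. The SAP takes the fatigue change from the infusion visit to that evening and to 15 days after the first infusion. Protocol 9.1.2 and Table 3 schedule the scale at the visit, that evening and the next day. These passages must be reconciled, so the fatigue time points should not be carried forward unexamined when the cell is rewritten.

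**The case against.** The strongest reply is that a controlling rule already exists. The manual clause opens the cell, and the disputed sentence can be read as subordinate to it. SAP 2.5 promises domain scores, and because the protocol calls the two summaries subscales formed from the domains, domain-level reporting could be taken to include them. The protocol endpoint asks only for SF-12 scores or responses. Nothing is tested, item responses are retained, and the SF-12 can be rescored later.

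Much of this stands, and it limits the weight of the point. It does not remove a specific instruction for a score that neither document defines. The domain promise is conditional and names no score. Protocol 9.9.2 assigns the detailed description of the analysis to the SAP, so the SAP is where the scores should be named.

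Three stronger readings are tempting but unsupported:

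- **That the SAP breaches the licensed manual or flatly contradicts itself.** The manual is not in the documents, so what it allows is unknown. Tension between adjacent sentences is as far as the text goes.
- **That the component summaries have been ruled out.** They are unnamed, not excluded; the manual clause would let an analyst report them.
- **That every questionnaire is mis-scored.** The documents give no ground to fault an item total for the WHO-5 or CSI. For the WPAI and WPAI:CG the sentences on totals do point to a score. What is missing is any statement that the manual defines such a total and that the planned change uses it.

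**Conclusion.** The point holds as a specification fault that should be corrected. SAP 2.6 calls for 1 SF-12 total that neither document defines, while the 2 component summaries described in the protocol are absent from the SAP. Taken literally, it would lead to an uninterpretable figure that blends the physical and mental sides. Domain and item results, where presented, would still show them separately.

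Its reach is confined to descriptive secondary endpoints: the SF-12 in about 120 patients and, less sharply, the score behind the planned WPAI and WPAI:CG changes. The primary endpoint and the study size are unaffected. The conclusion rests only on the wording of the two documents and assumes nothing about the content of the scoring manual.

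**What to change.** In SAP 2.6:

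- Limit the item-total sentence to instruments whose manual defines an item total.
- Name the SF-12 physical and mental component summaries, with the 8 domain scores, as the reported SF-12 scores. If an SF-12 total is wanted as well, it must at least be defined.
- Take the single-item fatigue scale out of the sentence. Take the WPAI out too, unless its manual defines a total.
- For both the WPAI and the WPAI:CG, name the manual-defined score or scores used for the planned change.
- Keep the item frequencies.
- Reconcile the fatigue change time points with Protocol 9.1.2 and Table 3 before restating them.
- Carry the named scores into the table shells, which are still open.

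The cost is a few lines of SAP text and the shells, with no new data. In the SF-12 table, 1 undefined total gives way to 2 component summaries. The item frequencies are already planned, and the 8 domain scores are planned where relevant.
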